1 PROTOCOL SYNOPSIS

Title: Efficacy and Safety of HemoStyp as an Adjunct for Management of Secondary Hemostasis in the Operative Setting

Protocol Number: UHP001

Investigational Device: HemoStyp

Sponsor: United Health Products, Inc.
[name]
[name]

Funding Organization: United Health Products, Inc.

Number of Sites: 10-15 sites

Number of Subjects: 236 subjects

Phase: Pivotal Study

Study Design: This study is a prospective, non-inferiority, multi-center, randomized, open-label trial to compare HemoStyp with Surgicel® in the management of bleeding during surgery.

Objectives: To assess efficacy and safety of HemoStyp as an adjunct for management of secondary hemostasis in the operative setting.

Subject Selection Criteria: Inclusion Criteria:
Subjects will be eligible to participate in this study if they meet all of the following criteria:

1. Elective procedure (non-laparoscopic thoracic, abdominal, or vascular surgery);
2. At time of surgery has mild to moderate soft tissue, vascular or parenchymal bleeding present at target bleeding site after primary standard conventional surgical hemostatic methods are proven to be ineffective or impractical;
3. Ages: Adult subjects ≥ 18 years of age; and
4. Subjects who are willing and able to sign consent.

Exclusion Criteria:
Subjects will not be eligible to participate in this study if they meet any of the following criteria:

1. Physical or psychological condition which would impair study participation;
2. Indications for emergency surgery;
3. Pre-operative laboratory findings of a hematologic disorder;
4. Subjects with history of moderate to severe allergies;
5. Subjects undergoing minimally invasive laparoscopic surgery;
6. Subjects who will require platelet or fresh frozen plasma transfusion during surgery;
7. Subjects who are pregnant or breast-feeding at the time of surgery; or
8. Subjects on P2Y12 platelet inhibitor (Plavix) less than 5 days prior to surgery, warfarin or Xa inhibitors not withheld per standard protocols for the management of anticoagulants pre-operatively.
9. Patients with a coagulation disorder, thrombocytopenia, liver disease and

anti-thrombin therapy.

Investigational Device/ Intended Use	HemoStyp is an absorbable hemostat composed of oxidized regenerated cellulose to be used as an adjunct to primary hemostasis in surgical procedures to assist in controlling capillary, venous and small arterial hemorrhage when other conventional methods are ineffective or impractical.
Control Group or Other Study Arms (if applicable)	Surgicel [®] Absorbable Hemostat (oxidized regenerated cellulose) is used adjunctively in surgical procedures to assist in the control of capillary, venous and small arterial hemorrhage when ligation or other conventional methods of control are impractical or ineffective.
Duration of Subject Participation and Study Duration:	Subjects will be in the study for up to 43 days Screening: Up to 10 days pre-operatively for elective surgery Treatment: Intra-operatively Follow-up: 30 days
Prohibited Concomitant Medications:	Anticoagulants, anti-platelets.
Efficacy Evaluations	
The primary performance endpoints include:
 
• Time to hemostasis from start of study treatment at target bleeding site until 10 minutes after treatment initiation. The non-inferiority of HemoStyp versus Surgicel will be evaluated. . 
Secondary efficacy endpoints include:
 
• Percentage of subjects achieving hemostasis at the target bleeding site at 2 minutes, 5 minutes and 10 minutes following the start of study treatment;• Percentage of subjects with intraoperative hemostasis at the target bleeding site;• Percentage of subjects with intraoperative re-bleeding from the target bleeding site post hemostasis; and• Percentage of subjects with postoperative re-bleeding from the target bleeding site requiring surgical re-exploration up to 30 days after surgery.
Safety Assessments:	Safety assessments will include evaluation of the frequency and nature of adverse events (AEs) and adverse device effects (ADEs) up to 30 days after treatment application.
Statistical Analyses:	
Sample Size A non-inferiority comparison will be performed to determine if the hazard ratio with an overall sample size of 212 subjects (106 HemoStyp group and 106 Surgicel group) achieves 80% power at a 0.05 significance level when the hazard ratio is actually 1.33 (median survival is 3.0 minutes for HemoStyp and 4.0 minutes for Surgicel). The non-inferiority ratio is 0.75 (corresponding to margin of 1 minute). It is anticipated that the proportion of subjects observed with the event during the study is 0.90 for the HemoStyp group and 0.92 for the Surgicel group. These results assume that the hazard ratio is constant throughout the study and that Cox proportional hazards regression or the non-inferiority log-rank test is used to analyze the data.
 
It is anticipated that approximately 710 subjects will be screened to randomize approximately 234 subjects with an anticipated drop-out rate of approximately 10%.

Efficacy Analyses

Analysis of Primary Endpoint

The time to hemostasis will be measured from start of study treatment to the achievement of hemostasis at the target bleeding site (TBS), or to the end of the 10-minute observation period. The time to hemostasis will be considered as censored at the end of the 10-minute observation period. Time to hemostasis will be quantified in minutes according to its nominal time point. When re-bleeding occurs, and the cessation of bleeding is again achieved at a later time point, the effective time to hemostasis will be the latter time point. The time to hemostasis will be the time from start of study treatment to that last effective hemostatic time point.

The primary endpoint analyses will be based on Intent-to-Treat (ITT) population. The primary analysis is the test of non-inferiority of HemoStyp compared with Surgical. The primary endpoint will be tested using Cox proportional hazards regression. The primary endpoint will be tested for superiority after the secondary endpoints have been analyzed. The primary endpoint analyses will also be performed on the Per Protocol (PP) population.

Analysis of Secondary Endpoint

A two-sided z-test with pooled variance will be used to test the difference for each secondary endpoint. The 95% confidence intervals (CIs) for each secondary endpoint in each group (HemoStyp or Surgical) will be provided. The secondary endpoints will be assessed at the significant level of 0.05 in a defined order after achievement of a significant result for the primary endpoint .

To assess homogeneity of treatment effectiveness, subgroup analyses will be performed.

Interim Analysis

After 118 randomized subjects have been seen at 30 day visit.

Safety Analyses

Safety analysis will be performed on the safety population using descriptive statistics without inferential tests for significance. Safety evaluation will include monitoring of adverse events (adverse events/serious adverse events [SAEs]) and adverse device effects (ADEs). Adverse events will be coded using the current version of the Medical Dictionary for Regulatory Activities (MedDRA). Treatment-emergent adverse events will be presented in summary tables by system organ class (SOC), preferred term and by treatment group. The number and percentage of subjects within each SOC and preferred term and the number of adverse events within each SOC and preferred term will be presented. The summary of adverse events by severity will be tabulated. The summary of adverse events by causality will also be provided. For each patient and each adverse event, the worst severity and causality recorded will be used in the by-intensity and by-relationship summaries.

Table 1.1 Schedule of Evaluations

	Screening	Surgery	Post-surgical Follow Up
Visit	V1	(Randomization) V2	V3
Trial Day	Day -10 to 0	Day 0	Day 30 ± 7
Informed consent	X		
Inclusion / Exclusion criteria	X	X	
Demographics	X		
Medical history	X		
Concomitant medication review	X	X	X
Vital signs	X		
Height and Weight	X		
Laboratory Measures ¹	X		
Urine pregnancy test ²	X		
Surgery performed		X	
Appropriate target bleeding sites identified ³		X	
Randomization		X	
Treatment applied to target bleeding sites		X	
Time to hemostasis of target bleeding sites		X	
Assess for re-bleeding or post-surgical re-bleeding		X-----X	X
Adverse events review		X	X

1. Laboratory parameters obtained for subjects as pre-operation standard of care that include a complete blood count (CBC) and may include prothrombin time (PT) and partial thromboplastin time (PTT) reflecting patients medical and medication history.

2. Obtained for women of child-bearing potential.

2 INTRODUCTION

Topical agents have been used to facilitate hemostasis for thousands of years, but remained largely ineffective in practice until the past century.¹ Advances in hemostatic technology have led to an assortment of products in the market today that are all capable of controlling bleeding. Topical hemostats are invaluable in surgery to control bleeding when conventional hemostatic methods such as ligature or cautery are impractical or ineffective. They were used in approximately 30% of surgical procedures in 2010², and that number continues to rise.

Choosing an adjunctive hemostatic agent not only requires evaluation of the situation in which a product will be applied, but also consideration of the product's efficacy, safety, ease of use, and affordability. In most cases, bioabsorbable hemostats are more desirable than non-absorbable hemostats because they do not have to be removed from the wound, which often results in re-bleeding. This is especially true for intraoperative use, where the consequences of re-bleeding are more severe, and it is much easier and safer to leave the hemostat on the wound to eventually be absorbed by the body.

HemoStyp (United Health Products, Inc.) is a patented bioabsorbable hemostatic gauze made from oxidized regenerated cellulose (ORC). Various forms of oxidized regenerated cellulose gauze have been available since 1942. The cellulose is obtained from cotton viscose and chemically treated to make it bioabsorbable, resulting in oxidized derivatized esterified cellulose. The end product is all natural, with no harmful chemicals or animal byproducts. It is a Class II medical device registered with the FDA to control bleeding in open wounds and in body cavities. Hemostyp is a sterile, woven, pH neutral gauze consisting of oxidized, esterified cellulose that is hypoallergenic and 100% water soluble. It is applied dry and as it absorbs blood it promptly turns into a gel, plugging the wound and providing a scaffold for the natural clotting process. The gel quickly dissolves into glucose and saline which is then harmlessly and easily absorbed by the body. It does not have to be removed from the wound. Any residue is easily removed with saline or can be left in the wound site to be absorbed.

Extensive research and laboratory testing has shown that Hemostyp is completely safe. pH testing was performed in January 2018 demonstrated a pH of 7.21. (reference—data on file) Dissolution studies have demonstrated that Hemostyp begins to dissolve in water within 1 minute and has total dissolution within 24 hours. (reference- data on file). Hemostyp is sterilized by radiation using conditions validated following ISO 11137-2: 2006 (ref data on file). Bioburden testing demonstrated an estimated burden of 43 cfu/unit. (ref data on file)

Additionally, in long-term animal studies of 3 weeks, necropsy results show that no Hemostyp was visible at the vessel site or under the skin, and the surrounding tissue appeared normal. The histopathology results showed an absence of neutrophils and a relatively quiescent leukocyte response in the tissues where Hemostyp was placed, indicating that the gauze was not contaminated with bacteria and that the immune response to the gauze was of minimal severity. Overall, Hemostyp performed as postulated, providing a lattice/scaffold to assist in clot formation and then being completely broken down and removed by the bodies systems without apparent harm (ref: data on file).

HemoStyp Mechanism of Action

The body relies on several mechanisms to achieve hemostasis. The first is primary hemostasis, that consists of vasoconstriction, which is the body's first response to injury in the vascular wall. When injury occurs, vessel walls constrict, causing reduced blood flow to the site of injury. HemoStyp enhances this recruiting process by absorbing water and other fluids from blood, making it viscous and slower moving, which also helps to minimize blood loss. Unlike most absorbable hemostats, HemoStyp is capable of increasing the viscosity of blood even in situations complicated by coagulation pathology or the use of anticoagulation drugs. This was demonstrated in an experiment in which HemoStyp initiated clotting in heparinized rabbit blood.²

The second method of primary hemostasis is platelet aggregation with the formation of a platelet plug. HemoStyp Hemostatic Gauze expedites hemostasis by creating an artificial clot that facilitates the natural blood clotting process. As it expands, it absorbs blood, entrapping blood proteins, platelets, and cells, essentially providing a scaffold for the natural clotting process. While this is happening, the gauze fibers begin to turn into a gel that plugs the wound, preventing further blood loss and providing a surface for platelet aggregation followed by solid fibrin clot formation.

Almost immediately after a blood vessel sustains an injury, platelets in the blood become activated, releasing chemicals that promote adhesion to other platelets and to blood vessel linings so that a platelet plug can be formed at the wound site. As such, the initial solid fabric state of HemoStyp gauze increases platelet aggregation at the wound site, expediting the formation of a platelet plug.

This is followed by secondary hemostasis. When bleeding is from larger vessels, blood clot formation is required. For blood coagulation to occur, the platelet plug is replaced with a stronger blood clot through a series of interdependent, enzyme-mediated reactions that bring about the generation of thrombin and the formation of fibrin from fibrinogen. This is accomplished through the intrinsic and extrinsic pathways. The intrinsic pathway starts with the conversion of clotting factor XII to its enzymatically active form, which is accomplished through contact with certain negatively charged surfaces. The negatively charged surface of HemoStyp ORC activates factor XII and initiates the intrinsic pathway of blood coagulation, leading to the formation of fibrin and thus enhancing another component of the hemostatic process. The activity of the intrinsic pathway can be measured by the partial thromboplastin test (PTT).

Hemostatic Efficacy

Research to date, has demonstrated the efficacy of HemoStyp Hemostatic Gauze in accelerating hemostasis. The PTT and the prothrombin time test (PT) measure the effectiveness of the intrinsic and extrinsic coagulation pathways, respectively. Blood mixed with HemoStyp was found to have significantly accelerated PTT and PT values, thus indicating its activity in enhancing both pathways.³⁻⁴ Additionally, HemoStyp gauze was able to achieve hemostasis in multiple studies in which the femoral artery was lacerated in a swine model.⁵⁻⁶ Swine are useful models because their cardiovascular systems are quite similar to

human's. As such, a laceration to the femoral artery, one of the largest vessels in the human and porcine body, is unable to produce hemostasis naturally before too much blood is lost. HemoStyp gauze achieved hemostasis consistently before fatal amounts of blood were lost, further demonstrating its efficacy.

Animal model research has shown that HemoStyp Hemostatic Gauze is equally or more effective than other available hemostats and current standard of care. One femoral artery study done in an animal model was a comparison to surgical lap sponges (non-absorbable gauze pads), and HemoStyp achieved hemostasis in significantly more swine.⁵ Another experiment found HemoStyp to be equally as effective in achieving hemostasis as Bloodstop (Lifescience), a more expensive type of ORC hemostat, in body surface and liver wounds in a rabbit model.² In vitro, HemoStyp was also found to have faster clotting times in a PT comparison to Surgicel[®] (Johnson & Johnson) the main commercial ORC in use today.⁴ HemoStyp also had faster clotting times in a PT comparison to Gelfoam (Pfizer) as well, which is a widely used gelatin-based hemostat made from porcine skin.⁴

Purpose of the Study

The purpose of this study is to demonstrate efficacy in the intra-operative setting in order to apply to the FDA for PMA Class III approval, which will allow HemoStyp to be used for intraoperative bleeding. HemoStyp recently obtained Class III and CE mark approval in the European Economic Area (EEA). This study is designed to evaluate the efficacy and safety of HemoStyp hemostatic gauze compared with Surgicel for the treatment of mild to moderate bleeding that arises during several types of surgery including general, cardio-thoracic, and vascular surgeries.. This study will use a validated bleeding severity scale that fulfills the FDA's requirements for a clinician-reported scale.⁸

Another study evaluated the time to hemostasis using HemoStyp in a swine liver punch model. Five Landrace X Yorkshire X Duroc crossbred healthy pigs were tested. After exposure of the liver, a 6 mm diameter biopsy punch by 7 mm depth lesion was created and the core was elevated with thumb forceps and cut with a # 15 blade. Dry gauze was immediately placed on the defect for a few seconds, upon removal, the HemoStyp was placed into and over the defect and wet (0.9% sodium chloride) gauze placed on the HemoStyp with mild pressure for 2.5 minutes. If hemostasis was not achieved, the dry gauze, HemoStyp with wet gauze cycle was repeated and time was recorded at 2.5, 5, and 10-minute increments for hemostasis. Five sites/insults were created and recorded for each animal. After 30 minutes post creation of the final punch, the animals were euthanized. The study results included all lesions with HemoStyp achieved hemostasis within the 10-minute limit. Almost all punch sites achieved hemostasis within the 2.5-minute range, and those that did not were due to surgeon error. All 20 defects achieved hemostasis with reapplication of HemoStyp. Results of this study suggest that properly placed HemoStyp will achieve hemostasis in liver tissue within 2.5 minutes for this type of lesion.⁹

3 STUDY OBJECTIVES

[figure not shown]
To assess efficacy and safety of HemoStyp as an adjunct for management of secondary hemostasis in the operative setting.

4 INVESTIGATIONAL PLAN

4.1 Overall Study Design and Plan

This study is a prospective, non-inferiority, multicenter, randomized, open-label trial to compare HemoStyp with Surgicel in the management of bleeding during surgeries.

Approximately 234 subjects will be randomized in a 1:1 ratio to either HemoStyp or Surgicel. Treatment randomization will be stratified by study centers and generated prior to study initiation. It is anticipated that approximately 710 subjects will be screened to enroll approximately 236 subjects with an anticipated drop-out rate of approximately 10%.

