11.1 Determination of Sample Size

A non-inferiority comparison will be performed to determine if the hazard ratio with an overall sample size of 212 subjects (106 HemoStyp group and 106 Surgicel group) achieves 80% power at a 0.05 significance level when the hazard ratio is actually 1.33 (median survival is 3.0 minutes for HemoStyp and 4.0 minutes for Surgicel). The non-inferiority ratio is 0.75 (corresponding to margin of 1 minute). It is anticipated that the proportion of subjects observed with the event during the study is 0.90 for the HemoStyp group and 0.92 for the Surgicel group. These results assume that the hazard ratio is constant throughout the study and that Cox proportional hazards regression or the non-inferiority log-rank test is used to analyze the data.

It is anticipated that approximately 710 subjects will be screened to randomize approximately 236 subjects with an anticipated drop-out rate of approximately 10%.

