14.15 Addendum 1: Summary of Changes

The original protocol was dated 10 September 2018. Amendment 1 (Version 1.2 Date: 02 July 2019) to the protocol provided clarification of study procedures and minor editorial changes. The following changes of key importance were implemented:

Interim Analysis:

Added: After 118 randomized subjects have been seen at 30 day visit.

Table 1.1:

Laboratory parameters obtained for subjects as pre-operation standard of care that include a complete blood count (CBC), prothrombin time (PT), and partial thromboplastin time (PTT) was changed to: **Laboratory parameters obtained for subjects as pre-operation standard of care that include a complete blood count (CBC) and may include prothrombin time (PT) and partial thromboplastin time (PTT) reflecting patients medical and medication history.**

Inclusion Criteria

Inclusion criteria were modified as follows

- 1. Elective procedure (non-laparoscopic thoracic, ~~cardiac~~, abdominal, or vascular surgery);
- 3. Ages: ~~Pediatric subjects ≥ 2 to 17 years of age and~~ adult subjects ≥ 18 years of age; and
- 4. ~~Subjects or parent or legal guardian of the subject~~ who are willing and able to sign consent.)

Statistical Analysis: Sample Size:

Sample size was changed from 236 to 234 throughout protocol

Sample size explanation was updated as follows:

It is anticipated that approximately 710 subjects will be screened to randomize approximately 236 subjects with an anticipated drop-out rate of approximately 10%.

With the omission of pediatric patients the protocol will attempt to equally randomize 54 patients across three surgical areas: Thoracic, abdominal and vascular surgery. Therefore the number randomized to each will increase from 60 to 78 subjects per group then randomizing approximately 29 to HemoStyp and Surgicel respectively.

Section 8.1 Informed consent

The following was deleted:

Pediatric Subjects

No pediatric subjects will be enrolled until a sample of at least 118 adult subjects have been enrolled and randomized in the study.

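### The current text gives two randomisation targets, 234 and 236, for the same 212 subjects and 10% drop-out; only 236 follows from dividing by 0.90 (minor)

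*Combined protocol and SAP*

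**What the plan says.** The randomisation target appears in four parts of the current text, and the values disagree.

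- Synopsis, header entry: "Number of Subjects: 236 subjects".
- Synopsis, sample-size text: "screened to randomize approximately 234 subjects with an anticipated drop-out rate of approximately 10" per cent.
- Section 4.1: "Approximately 234 subjects will be randomized in a 1:1 ratio to either HemoStyp or Surgicel", followed two sentences later by "screened to enroll approximately 236 subjects with an anticipated drop-out rate of approximately 10" per cent.
- Section 11.1: "It is anticipated that approximately 710 subjects will be screened to randomize approximately 236 subjects with an anticipated drop-out rate of approximately 10" per cent.

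The synopsis sample-size text and section 11.1 carry the same power statement. In section 11.1 it reads "overall sample size of 212 subjects (106 HemoStyp group and 106 Surgicel group) achieves 80% power at a 0.05 significance level". No other basis for 234 or 236 is given in the operative sections.

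**The concern.** A planned sample size should have one value. Here it depends on which page is read, and section 4.1 alone gives both values. The randomisation list is to be generated before the study starts (section 4.1), with sealed envelopes by arm and centre (section 4.1.1). Whoever prepares the list and closes enrolment needs a single number. In an open-label trial it is better that the end of recruitment is not left to interpretation, even by two subjects. The two figures also do not fit the stated basis equally well: one reproduces from 212 and 10%, and the other falls slightly short.

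**Working it through.** **Inputs.** 212 subjects in total and 106 per arm (section 11.1 and synopsis); drop-out about 10% (synopsis, sections 4.1 and 11.1); true hazard ratio 1.33, margin 0.75, and event proportions 0.90 and 0.92, mean 0.91 (section 11.1). Whether the 0.05 level is one- or two-sided is not stated there, so one-sided 0.05 and 0.025 were both tried.

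**Step 1: reproduce the targets.** To have N subjects left after a loss of fraction d, randomise N/(1 − d).

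- Total: 212/0.90 = 235.6, so 236. Per arm: 106/0.90 = 117.8, so 118. The figure of 236 reproduces.
- Multiplying instead of dividing gives 212 × 1.10 = 233.2, so 234. That is a common slip and a possible origin of 234. But 234 is also 3 × 78, a per-area figure in the Summary of Changes (section 14.15), and the documents do not say where it came from.

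**Step 2: expected number after 10% loss.**

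| Target | × 0.90 | Per arm | Against 212 |
|---|---|---|---|
| 234 | 210.6 | 105.3 | 1.4 short (0.7%) |
| 236 | 212.4 | 106.2 | 0.4 over |

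The drop-out at which 234 still leaves 212 is 1 − 212/234 = 9.4%.

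**Step 3: effect on power.** By the Schoenfeld approximation for a non-inferiority log-rank test, power = Φ(√(E/4) × ln(HR/margin) − z), with E = 0.91 × N events. At HR 1.33, margin 0.75 and one-sided 0.025 (z = 1.96):

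- N = 212: E = 192.9, power 97.82%.
- N = 210.6: E = 191.6, power 97.75%.
- N = 212.4: E = 193.3, power 97.84%.

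The calculation was repeated with true hazard ratios of 1.0 and 1.33, margins of 0.75, 0.80 and 1.0, and one-sided levels of 0.05 and 0.025. The loss from 212 to 210.6 stays under 0.3 percentage points throughout. The largest difference between the two targets after 10% loss is 51.59% − 51.25% = 0.34 points (true HR 1.0, margin 0.75, one-sided 0.025).

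**Step 4: does the power statement require 212?** The events needed for 80% power are 4 × ((z_α + z_β)/ln(HR/margin))². With HR 1.33, margin 0.75 and one-sided 0.025 this is 95.7 events, and 95.7/0.91 = 105.1, so 106 subjects in total. At one-sided 0.05 it is 75.4 events, or 83 subjects in total. The 212 is therefore the number the plan states, not one that its inputs require.

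**The case against.** The strongest defence is that nothing of substance turns on two subjects. Both the target and the drop-out rate are given as approximate, the shortfall under 234 is 1.4 subjects, and section 6.4 allows withdrawn subjects to be replaced. The primary endpoint is observed within 10 minutes during surgery and analysed by intention to treat (sections 11.2.2 and 11.2.5), so loss before Day 30 removes no primary data. Only randomised but untreated subjects could be lost, through the restriction to treated subjects in section 11.2.7. All of this stands as an argument about size, and it is why the point is rated minor. Drop-out still matters somewhat for the per-protocol analysis, which needs complete scheduled data, and for 30-day re-bleeding.

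The defence does not remove the inconsistency. Reading section 4.1 as 236 enrolled and 234 randomised fails, because section 11.1 applies the verb *randomize* to 236 and the synopsis applies it to 234 in the same sentence. The word *approximately* does not explain two values for one quantity, and the synopsis header gives 236 without it. Replacement is optional and does not fix the target.

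It can also be argued that 234 is the intended number, since the Summary of Changes records a move from 236 to 234. That log describes superseded text, and its own updated sentence still gives 236. It is not counted here as an error, and it does not settle which figure is meant.

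**Conclusion.** The point holds as a minor correction. The operative text gives two targets, and only 236 follows from 212 and a 10% loss by division. The shortfall under 234 is 1.4 subjects, with negligible effect on power. The arithmetic assumes that 212 is meant as the number remaining after loss and that drop-out is 10%.

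Three stronger readings are tempting, and the documents do not support them.

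- A reader might infer that 234 leaves the trial short of what the power statement needs. It does not: on the stated inputs about 106 subjects in total give 80% power at one-sided 0.025, so 212 itself does not reproduce. That is a separate question about the sample-size basis.
- A reader might infer that the interim trigger, "After 118 randomized subjects have been seen at 30 day visit", proves 236 because 118 is half of it. No section describes the trigger as half the sample, and a trigger of 118 is workable under either total.
- A reader might add the per-area split, "the number randomized to each will increase from 60 to 78 subjects per group then randomizing approximately 29 to HemoStyp and Surgicel respectively". It is true that 78/2 = 39, not 29. But that sentence stands only in the Summary of Changes, and randomisation is stratified by centre, so no operative quota depends on it.

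**What to change.** State one target in the synopsis header, the synopsis sample-size text, section 4.1 and section 11.1, with its derivation in half a sentence.

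- If 212 after 10% loss is intended, use 236 (118 per arm). This changes the synopsis sample-size text and the first figure in section 4.1.
- If 234 is intended, change the synopsis header, the second figure in section 4.1 and section 11.1. Restate the expected number after loss as about 210 (105 per arm), with the power recomputed for that number.

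The sponsor must say which is meant, because the documents do not. The cost is a text correction in the next amendment and at most two subjects, who are already within the 236 given in the synopsis header and section 11.1.
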